3.1 STUDY PARAMETERS

3.1.1 Safety Parameters

The safety of acalabrutinib and pembrolizumab will be characterized by the type, frequency, severity, timing of onset, duration, and relationship to study drug(s) of any treatment-emergent AEs or abnormalities of laboratory tests; SAEs; DLTs or AEs leading to discontinuation of study treatment.

3.1.2 Pharmacodynamic, Pharmacokinetic and Biomarker Parameters

The occupancy of BTK by acalabrutinib will be measured in PBMCs with the aid of a biotin-tagged acalabrutinib analogue probe. The effect of acalabrutinib and pembrolizumab on B cells, T cells and MDSCs will also be evaluated. Tumor tissue, when available, will be evaluated for PD-L1 expression. Additional exploratory correlative studies of tumor tissue, when available, may include characterization of tumor subtypes by immunohistochemistry, gene expression or mutation analysis.

The following PK parameters will be calculated, whenever possible, from plasma concentrations of acalabrutinib:

- $AUC_{0\text{-last}}$: Area under the plasma concentration-time curve calculated using linear trapezoidal summation from time 0 to time last, where “last” is the time of the last measurable concentration.
- $AUC_{0\text{-}12}$: Area under the plasma concentration-time curve from 0 to 12 hours, calculated using linear trapezoidal summation.
- $AUC_{0\text{-}inf}$: Area under the plasma concentration-time curve from 0 to infinity, calculated using the formula: $AUC_{0\text{-}inf} = AUC_{0\text{-}last} + C_{last} / \lambda_z$, where λ_z is the apparent terminal elimination rate constant.
- $AUC_{0\text{-}24\text{calc}}$: Area under the plasma concentration-time curve from 0 to 24 hours, calculated by doubling the value for $AUC_{0\text{-}12}$
- C_{max} : Maximum observed plasma concentration
- T_{max} : Time of the maximum plasma concentration (obtained without interpolation)
- $t_{1/2}$: Terminal elimination half-life (whenever possible)
- λ_z : Terminal elimination rate constant (whenever possible)
- CL/F : Oral clearance
- Vz/F : Oral volume of distribution

3.1.3 Efficacy Parameters

Efficacy will be evaluated based on assessments of tumor response and progression using the standardized RECIST, Version 1.1 ([Eisenhauer 2009](#); [Appendix 7](#)).

Efficacy endpoints will include:

- Overall response rate (ORR)
- Disease control rate (DCR)
- Duration of response (DOR)
- Progression-free survival (PFS)
- Overall survival (OS)

Efficacy endpoints will include:

- irORR (irCR + irPR)
- irDCR (irCR + irPR + irSD)
- irDOR
- irPFS

3.2 RATIONALE FOR STUDY DESIGN AND DOSING REGIMEN

As described in [Section 1.7](#), acalabrutinib is currently being evaluated in a Phase 1/2 study in subjects with CLL (ACE-CL-001). In this study, subjects have received oral dosages of 100 to 400 mg QD and 100 to 200 mg BID of acalabrutinib. All tested dose levels have been well tolerated:

- No MTD has been reached.
- No DLT has occurred at any dose level.
- No study-drug related AE has led to discontinuation from the study.
- No study-drug related SAEs have occurred.

Robust clinical responses have been observed with dosages as low as 100 mg QD.

Preliminary PK data from ACE-CL-001 suggests a plateauing of exposure after 250 mg QD. PD results from this study also show 100 and 200 mg BID have the highest BTK occupancy at 24 hours of all the regimens evaluated.

The dose of pembrolizumab planned to be studied in this trial is 200 mg Q3W. The dose recently approved in the United States and several other countries for treatment of melanoma subjects is 2 mg/kg Q3W. Information on the rationale for selecting 200 mg Q3W is summarized below.

KEYNOTE-001 was an open-label Phase 1 study conducted to evaluate the safety, tolerability, PK and PD, and anti-tumor activity of pembrolizumab when administered as monotherapy. The dose escalation portion of this trial evaluated 3 dose levels, 1 mg/kg, 3 mg/kg and 10 mg/kg, administered every 2 weeks (Q2W) and dose expansion cohorts evaluated 2 mg/kg Q3W and 10 mg/kg Q3W in subjects with advanced solid tumors. All dose levels were well tolerated and no DLTs were observed. This first-in-human study of pembrolizumab showed evidence of target engagement and objective evidence of tumor size reduction at all dose levels. No MTD has been identified. In addition, 2 randomized cohort evaluations of melanoma subjects receiving pembrolizumab at a dose of 2 mg/kg versus 10 mg/kg Q3W have been completed, and 1 randomized cohort evaluating 10 mg/kg Q3W versus 10 mg/kg Q2W has also been completed. The clinical efficacy and safety data demonstrate a lack of important differences in efficacy or safety profile across doses.

An integrated body of evidence suggests that 200 mg Q3W is expected to provide similar response to 2 mg/kg Q3W, 10 mg/kg Q3W and 10 mg/kg Q2W. Previously, a flat pembrolizumab exposure-response relationship for efficacy and safety has been found in subjects with melanoma in the range of doses between 2 mg/kg and 10 mg/kg. Exposures for 200 mg Q3W are expected to lie within this range and will be close to those obtained with 2 mg/kg Q3W dose.

A population pharmacokinetic (PK) model, which characterized the influence of body weight and other patient covariates on exposure, has been developed. The PK profile of pembrolizumab is consistent with that of other humanized monoclonal antibodies, which typically have a low clearance and a limited volume of distribution. The distribution of exposures from the 200 mg fixed dose are predicted to considerably overlap those obtained with the 2 mg/kg dose and importantly will maintain individual patient

exposures within the exposure range established in melanoma as associated with maximal clinical response. Pharmacokinetic properties of pembrolizumab, and specifically the weight-dependency in clearance and volume of distribution are consistent with no meaningful advantage to weight-based dosing relative to fixed dosing.

In translating to other tumor indications, similarly flat exposure-response relationships for efficacy and safety as observed in subjects with melanoma can be expected, as the anti-tumor effect of pembrolizumab is driven through immune system activation rather than through a direct interaction with tumor cells, rendering it independent of the specific tumor type. In addition, available PK results in subjects with melanoma, NSCLC, and other tumor types support a lack of meaningful difference in pharmacokinetic exposures obtained at tested doses among tumor types. Thus the 200 mg Q3W fixed-dose regimen is considered an appropriate fixed dose for other tumor indications as well.

A fixed dose regimen will simplify the dosing regimen to be more convenient for physicians and to reduce potential for dosing errors. A fixed dosing scheme will also reduce complexity in the logistical chain at treatment facilities and reduce wastage. The existing data suggest 200 mg Q3W as the appropriate dose for pembrolizumab.

As described in [Section 1.4](#), Acerta Pharma has conducted a nonclinical study to evaluate the potential synergy of BTK inhibition with PD-1 blockade and has seen encouraging results, which warrant testing the hypothesis in a clinical trial.

3.3 SELECTION OF STUDY POPULATION

3.3.1 Inclusion Criteria

Eligible subjects will be considered for inclusion in this study if they meet **all** of the following criteria:

1. Men and women \geq 18 years of age.
2. Histologically confirmed recurrent or metastatic NSCLC (adenocarcinoma, large cell, squamous cell, or not otherwise specified). SCLC or mixed SCLC/NSCLC are not permitted.
- 3a) Disease that has either progressed during or after platinum-based chemotherapy administered for metastatic disease or has recurred during or within 6 months after the completion of platinum-based neoadjuvant or adjuvant therapy. Or,
- 3b) Subjects with EGFR mutations or ALK translocations are required to have received prior therapy with appropriate TKI; prior platinum-based chemotherapy is not required for this specific patient population.
4. Presence of radiographically measurable disease as defined by RECIST 1.1.
5. ECOG performance status of 0 or 1.

6. Completion of all therapy (including surgery, radiotherapy, chemotherapy, immunotherapy, or investigational therapy) for the treatment of cancer \geq 2 weeks before the start of study therapy and recovered (ie, Grade \leq 1 or baseline) from AEs associated with prior cancer therapy. Note: Subjects with Grade \leq 2 neuropathy or Grade \leq 2 alopecia are an exception to the latter criterion and may qualify for the study.
7. Women who are sexually active and can bear children must agree to use acceptable forms of contraception during the study and for 90 days after the last dose of acalabrutinib or 120 days after the last dose of pembrolizumab, whichever is longer. Note: Acceptable forms of contraception are defined in [Section 3.10.6](#).
8. Men who are sexually active and can beget children must agree to use acceptable forms of contraception during the study and for 90 days after the last dose of acalabrutinib or 120 days after the last dose of pembrolizumab, whichever is longer.
9. Men must agree to refrain from sperm donation during the study and for 90 days after the last dose of acalabrutinib or 120 days after the last dose of pembrolizumab, whichever is longer.
10. Able to provide tissue for biomarker analysis from either an archived tissue sample or newly obtained core or excisional biopsy of a tumor lesion not previously irradiated.
11. Willing and able to participate in all required evaluations and procedures in this study protocol including swallowing capsules without difficulty.
12. Ability to understand the purpose and risks of the study and provide signed and dated informed consent and authorization to use protected health information (in accordance with national and local patient privacy regulations).

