	
angiogenesis (Condamine 2014). Therefore, MDSCs can be a mechanism of resistance to anti-PD-1 therapy. When used in combination with checkpoint inhibitors, agents that inhibit MDSCs can improve outcomes in murine models of metastatic disease (Kim 2014).
 
Bruton tyrosine kinase (BTK) is a non-receptor enzyme of the Tec kinase family that is expressed in B cells, myeloid cells, and mast cells, where it regulates cellular proliferation, differentiation, apoptosis, and cell migration. BTK inhibition leads to preferential differentiation of macrophages into M1 instead of immunosuppressive M2 macrophages; BTK inhibition thus decreases the tumor-associated macrophages that promote tumor invasion and metastasis.
 
Acerta Pharma BV is developing acalabrutinib, an orally administered, small-molecule inhibitor of BTK. A Phase 1 study of acalabrutinib in 60 subjects with relapsed/refractory chronic lymphocytic leukemia showed an overall response rate of 95%. Acalabrutinib monotherapy has shown robust antitumor activity in murine solid tumor models. The antitumor effect observed with acalabrutinib correlates with biomarkers of response similar to those reported for other immunomodulating agents such as inhibitors of CTLA-4, PD-1 and PD-L1.
 
To determine whether there is potential synergy between BTK inhibition and PD-1 blockade, Acerta has conducted a nonclinical study of acalabrutinib in combination with an anti-PD ligand 1 (anti-PD-L1) antibody in an orthotopic colon cancer murine model. Treatment with anti-PD-L1 as a single agent reduced tumor growth, but tumor regression was not observed. However, combined anti-PD-L1 and acalabrutinib treatment showed a further reduction in tumor growth. Specifically, 6 of 9 animals displayed tumor regression compared with no animals treated with anti-PD-L1 alone (Figure 1-9). These results suggest the combination therapy of BTK inhibition and PD-1 blockade leads to greater benefit compared with PD-1 blockade alone.
 
This proof-of-concept study will assess the clinical potential of a targeted dual inhibition approach by evaluating the safety, pharmacodynamics (PD), pharmacokinetics (PK), and efficacy of acalabrutinib and pembrolizumab in subjects with advanced, previously treated NSCLC.

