Efficacy Endpoints:	
 • ORR, defined as partial response (PR) and complete response (CR), based on modified RECIST 1.1 criteria (Appendix 7) • Disease control rate (DCR), defined as CR, PR, and stable disease (SD) based on modified RECIST 1.1 criteria • Duration of response (DOR) • Progression-free survival (PFS) • Overall survival (OS)      
Sample Size:	    
Inclusion Criteria:	
 1. Men and women \geq 18 years of age. 2. Histologically confirmed recurrent or metastatic NSCLC (adenocarcinoma, large cell, squamous cell, or not otherwise specified). Small cell lung cancer (SCLC) or mixed SCLC/NSCLC are not permitted. 3a) Disease that has either progressed during or after platinum-based chemotherapy administered for metastatic disease or has recurred during or within 6 months after the completion of platinum-based neoadjuvant or adjuvant therapy. Or,

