	
3b) Subjects with epidermal growth factor receptor (EGFR) mutations or alkaline phosphatase (ALK) translocations are required to have received prior therapy with appropriate tyrosine kinase inhibitor (TKI); prior platinum-based chemotherapy is not required for this specific patient population.
 
 4. Presence of radiographically measurable disease as defined by RECIST 1.1. 5. Eastern Cooperative Oncology Group (ECOG) performance status of 0 or 1. 6. Completion of all therapy (including surgery, radiotherapy, chemotherapy, immunotherapy, or investigational therapy) for the treatment of cancer \geq 2 weeks before the start of study therapy and recovered (ie, Grade \leq 1 or baseline) from AEs associated with prior cancer therapy. Note: Subjects with Grade \leq 2 neuropathy or Grade \leq 2 alopecia are an exception to the latter criterion and may qualify for the study. 7. Women who are sexually active and can bear children must agree to use acceptable forms of contraception during the study and for 90 days after the last dose of acalabrutinib or 120 days after the last dose of pembrolizumab, whichever is longer. Note: Acceptable forms of contraception are defined in Section 3.10.6. 8. Men who are sexually active and can beget children must agree to use acceptable forms of contraception during the study and for 90 days after the last dose of acalabrutinib or 120 days after the last dose of pembrolizumab, whichever is longer. 9. Men must agree to refrain from sperm donation during the study and for 90 days after the last dose of acalabrutinib or 120 days after the last dose of pembrolizumab, whichever is longer. 10. Able to provide tissue for biomarker analysis from either an archived tissue sample or newly obtained core or excisional biopsy of a tumor lesion not previously irradiated. 11. Willing and able to participate in all required evaluations and procedures in this study protocol including swallowing capsules without difficulty. 12. Ability to understand the purpose and risks of the study and provide signed and dated informed consent and authorization to use protected health information (in accordance with national and local patient privacy regulations).

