3.3.4 Enrollment and Randomization Procedures

Enrollment of a subject into the study will be performed according to the following procedure:

The study center will notify the sponsor when a clinically eligible subject is identified and is ready to screen, to ensure enrollment availability on the study.

After the subject has signed and dated the Informed Consent Form (ICF), all screening procedures have been completed, and eligibility has been confirmed, the subject can be officially enrolled into the study.

To enroll a subject, the study center will fax/email a completed Enrollment Confirmation Form to the sponsor. The enrollment date will be the date that the sponsor confirms enrollment. The sponsor will aim to fax/email a completed Enrollment Confirmation Form to the study center within 24 hours.

The treatment assignment is based on the randomization list generated by the sponsor before study enrollment begins.

The Enrollment Confirmation Form will contain treatment-arm allocation.

Treatment must begin within the screening window ([Section 4.1](#)) and after the site has received the treatment-arm allocation from the sponsor.

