4.1.5 Confirmation of Eligibility

Subject eligibility for enrollment will be assessed per [Section 3.3](#). All screening procedures, unless otherwise indicated, should be completed within 28 days of the first dose of study drug.

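### Inclusion criterion 3b asks EGFR/ALK subjects only to have received a TKI, so one who stops a still-effective TKI is eligible as written; the 'Or' before 3b also leaves the TKI-naive case unsettled

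*Protocol*

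**What the plan says.** Criterion 3a in Section 3.3.1 sets a progression condition: "Disease that has either progressed during or after platinum-based chemotherapy administered for metastatic disease", or disease that "recurred during or within 6 months after the completion of platinum-based neoadjuvant or adjuvant therapy. Or". The closing 'Or' leads into 3b: "Subjects with EGFR mutations or ALK translocations are required to have received prior therapy with appropriate TKI". Criterion 3b then states that platinum is not needed for these subjects. The synopsis carries the same rule: EGFR/ALK subjects "are required to have received prior therapy with appropriate tyrosine kinase inhibitor (TKI").

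Criterion 6 asks for "Completion of all therapy (including surgery, radiotherapy, chemotherapy, immunotherapy, or investigational therapy) for the treatment of cancer" at least 2 weeks before study therapy, with recovery from the adverse events of that therapy. It does not ask why the therapy ended.

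Section 4.1.5 says "Subject eligibility for enrollment will be assessed per" Section 3.3. Section 3.3.4 says that once "all screening procedures have been completed, and eligibility has been confirmed, the subject can be officially enrolled into the study". The synopsis background describes the population as "subjects with advanced, previously treated NSCLC", which speaks of prior treatment and not of prior failure.

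Section 1.8 and the label in Appendix 6 (its Section 1.2) give the US lung-cancer indication. Both say that patients with EGFR or ALK aberrations should have progressed on approved therapy for those aberrations before receiving pembrolizumab.

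**The concern.** Subjects who enter through 3a must have failed platinum. Subjects who enter through 3b need only have been exposed to a TKI. Read literally, the protocol lets a subject give up a targeted drug that is still working in order to join a proof-of-concept study. The protocol's own account of the indication points the other way. Criterion 3b openly announces that it drops the platinum condition. It does not announce that it drops TKI progression, and the design rationale in Section 3.2 covers dose and drug synergy only.

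A second, smaller problem is the link between 3a and 3b. 'Or' suggests that meeting either one is enough, whereas 3b makes a TKI compulsory for the EGFR/ALK group. With up to 20 centers, a rule with two readings can be applied in two ways.

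What is at stake is protection of a small group of subjects and uniform eligibility, not the trial's statistical properties.

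**Working it through.** The plan gives no figure on this point, so the check is a reading of the criteria against each other.

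**Step 1: is the missing condition supplied elsewhere?** Among the 12 inclusion and 27 exclusion criteria, 3a is the only one that demands progression or recurrence after a prior treatment.
- Criterion 2 accepts recurrent or metastatic disease, so metastatic disease alone is enough.
- Criterion 4 asks for measurable disease, which stable or partially responding disease can satisfy.
- Criterion 6 asks that therapy be completed, not that it failed.
- No exclusion criterion addresses disease controlled on a TKI.
- Sections 3.3.4 and 4.1.5 apply the Section 3.3 criteria and add none of their own.

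**Step 2: apply the text to EGFR/ALK treatment histories.** All other criteria are assumed met, including the 2-week interval. The second answer applies the wording proposed under the fix.
- Progressed on a TKI, no platinum: eligible; stays eligible.
- Intolerant to a TKI without progression, no platinum: eligible; stays eligible.
- TKI, then progression on platinum: eligible; stays eligible.
- Stopped a still-effective TKI, no platinum: eligible through 3b; becomes ineligible.
- Progressed on a first TKI, then stopped a still-effective second one: eligible through 3b; becomes ineligible, because the condition is tied to the most recent TKI.
- TKI-naive, progressed on platinum: eligible by 'Or', ineligible by the TKI requirement in 3b; becomes ineligible.

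These histories illustrate how the rule works. They are not a measure of how often each case would occur.

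**Step 3: compare with the protocol's own source.** The indication in Section 1.8 places two progression conditions on an EGFR/ALK patient: on platinum and on targeted therapy. Criterion 3b removes both and says so for only one.

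**Step 4: does any design input move?** The sample size rests on projected response rates of 40% and 18%, one-sided alpha 0.10 and 80% power. The unpooled normal approximation gives n = (1.2816 + 0.8416)² × (0.40×0.60 + 0.18×0.82) / 0.22² = 36.1, so 37 per arm, matching the synopsis maximum of 37. The wording of 3b does not enter this calculation.

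**The case against.** The strongest reply is that the case will hardly arise. Criterion 6 shuts out anyone still taking a TKI, and few investigators or patients would stop a working drug for an untested combination. Section 1.8 and the label already tell investigators what the norm is. The trial also departs from the label elsewhere, with a flat 200 mg dose and no PD-L1 selection, so a broader 3b could be deliberate.

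Much of this stands. A reader might infer from 3b that a subject can enter while still on a TKI; criterion 6 rules that out. Only a subject who has already stopped can qualify. But criterion 6 asks for no reason for stopping, Section 1.8 is background and not an eligibility rule, and no rationale for dropping TKI progression is given. The flat dose, by contrast, is argued at length in Section 3.2.

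On the TKI-naive case, the objection is that 3b is the specific and mandatory clause, so 3a is for other subjects and 3b for EGFR/ALK subjects. That is the more natural reading. Enrollment is also confirmed by one sponsor, which gives a single place to resolve a query. Even so, Section 3.3.4 describes no eligibility ruling by the sponsor, and 'Or' still says something different.

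A reader might also fault 3b for admitting a subject who progressed on platinum and was then controlled on a later TKI. That subject qualifies under 3a whatever 3b says, since 3a does not ask about the latest line of therapy. It is not a defect of 3b.

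**Conclusion.** The point holds as a minor eligibility defect. As written, an EGFR/ALK subject who stops a still-effective TKI at least 2 weeks before study therapy is eligible, contrary to the indication that the protocol itself cites. The status of the TKI-naive, platinum-progressed subject is not settled, although the text leans towards requiring a TKI.

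The documents give no number or share of EGFR/ALK subjects, so the number affected is unknown and may be zero. A reader might infer that such subjects would distort the response rates or cost power. The documents do not support that: no effect is shown, randomization gives no reason to expect a systematic difference between arms, and no sample-size input depends on 3b.

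The conclusion rests on reading the criteria literally and on taking Section 1.8 and the label as the protocol's own benchmark for this group. If the sponsor meant to admit these subjects, the defect is that the choice is neither stated nor justified.

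**What to change.** In Section 3.3.1 and in the synopsis, replace the 'Or' and 3b with:

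> Subjects without a known EGFR mutation or ALK translocation must meet 3a. Subjects with an EGFR mutation or ALK translocation must have received an appropriate TKI and must have had disease progression on, or intolerance to, the most recent appropriate TKI, or have met 3a after it; prior platinum-based chemotherapy is not otherwise required for this population.

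This keeps the platinum waiver, admits TKI-intolerant subjects, covers sequential TKIs and settles the TKI-naive case. If the sponsor wants TKI-naive, platinum-progressed subjects, it can say so instead; either answer removes the ambiguity.

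The cost is one short edit in two places. Progression on a TKI can be checked from the prior treatments and responses already collected under Section 4.1.2; intolerance may need one added line on the form. A few candidates are lost: those who stopped a TKI without progression or intolerance and have not since met 3a, including after earlier platinum failure, and those who are TKI-naive. Optionally, list any enrolled EGFR/ALK subjects without documented TKI progression or intolerance.
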